**Overview of rationale and Study Design:**

In this phase I study, escalating doses of ixazomib will be combined with the VXD regimen.

The MTD of single agent ixazomib was 1.76 to 2.0mg/m^2 when given on a twice a week schedule and > 2.34 mg/m^2 to 2.97 mg/m^2 on a weekly schedule in previous studies. The only reported combination study involved the combination of ixazomib with lenalidomide and dexamethasone. In that study, escalating doses of IXAZOMIB from 1.68 to 3.95 mg/m^2 were given orally on days 1, 8, and 15 in combination with dexamethasone 40 mg on days 1, 8, 15, and 22 and lenalidomide 25 mg/day on days 1–21 every 28 Days. The MTD of ixazomib was 2.97 mg/m^2 and the recommended phase II dose (RP2D) was 2.23 mg/m^2. The dose limiting toxicities were skin rash, nausea and vomiting. The clinical development of ixazomib included a population PK analysis evaluating the feasibility of switching from BSA-based dosing to fixed dosing. The results of this analysis support the transition to fixed dosing. In this trial our aim will be to escalate the dose to ixazomib orally to a dose of 4.0 mg (RP2D of 2.23 mg/m^2 × the mean patient BSA of 1.86 m^2).

Three patients will be treated per dose level unless dose limiting toxicity (DLT) is observed. The starting dose of ixazomib will be 2.3 mg orally on days 1, 8 and 15. If no DLT is seen in the first 3 patients, the dose will be increased to 3 mg and then to 4 mg orally on days 1, 8 and 15 in a classic 3 +3 phase I design. We will not attempt to increase the dose beyond 4 mg orally which, if achieved with acceptable toxicity, would be accepted as the recommended phase 2 dose (RP2D). 0 of 3 DLTs would allow escalation to the next dose level. 1 of 3 DLTs will require expanding to six patients; 1 of 6 DLTs will allow escalation again. 2 DLTs will require dose de-escalation. The maximum tolerated dose (MTD) will be the highest dose administered at which no more than 1 DLT was observed. All patients will be evaluated for hematopoietic stem cell transplantation (HSCT). If patients achieve CR and are eligible for HSCT, they will proceed to HSCT. If they

are not eligible, no donor is identified or if HSCT will be delayed, and the patient has achieved benefit, then treatment may be repeated for another cycle as clinically indicated.

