#### Exclusion criteria

- Patients who are Ph+ ALL who are naive to therapy with an approved tyrosine kinase inhibitor.
- Prior exposure to  $\geq 350$  mg/m^2 of anthracycline (in doxorubicin equivalent dosing), or left ventricular fractional shortening less than 50%.
- Failure to have fully recovered (ie,  $\leq$  Grade 2 toxicity) from the effects of prior chemotherapy regardless of the interval since last treatment.
- Major surgery within 14 days before enrollment.
- Chemotherapy in the last 14 days. (Steroids or Intrathecal chemotherapy will be allowed).

- Systemic treatment, within 7 days before study enrollment, with strong inhibitors of CYP1A2 (fluvoxamine, enoxacin, ciprofloxacin), strong inhibitors of CYP3A (clarithromycin, telithromycin, itraconazole, voriconazole, ketoconazole, nefazodone, posaconazole) or strong CYP3A inducers (rifampin, rifapentine, rifabutin, carbamazepine, phenytoin, phenobarbital), or use of Ginkgo biloba or St. John's wort.
- Uncontrolled intercurrent illness including, but not limited to ongoing or active infection, symptomatic congestive heart failure, or psychiatric illness/social situations that would limit compliance with study requirements. Patients receiving intravenous antibiotics for infections that are under control may be included in this study.
- Known allergy to any of the study medications, their analogues, or excipients in the various formulations of any agent.
- Inability to swallow oral medication, inability or unwillingness to comply with the drug administration requirements, or GI procedure that could interfere with the oral absorption or tolerance of treatment.
- Diagnosed or treated for another malignancy within 2 years before study enrollment or previously diagnosed with another malignancy and have any evidence of residual disease. Patients with nonmelanoma skin cancer or carcinoma in situ of any type are not excluded if they have undergone complete resection.
- Patient has  $\geq$  Grade 2 peripheral neuropathy.
- Participation in clinical trials with other investigational agents not included in this trial, within 14 days of the start of this trial and throughout the duration of this trial.

- Female patients who are breastfeeding or have a positive serum pregnancy test during the screening period or a positive urine pregnancy test on Day 1 before first dose of study drug.

**Duration of Study:** A minimum of 2 years

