### SCHEDULE OF EVENTS

Day	Screening a	Cycle 1 and 2 Week 1	Weekly	Q 2 weeks	Q 4 weeks	End of Study b	Follow-up
Informed consent	X						
Demographics	X						
Inclusion/exclusion criteria	X						
Medical History	X	X					
Medication history	X						
Concomitant medications	X	X		X		X	
Physical examination	X	X		X		X	
ECOG performance status	X	X		X			
Vitals	X	X		X		X	
Height and weight c	X	X d				X	
CBC with differential	X	X	X			X	
Serum Chemistry	X	X	X			X	

panel e							
Direct Bilirubin	X		X				
Fibrinogen	X	X	X				
Serum or urine pregnancy test	X	X f					
Cardiac Ejection Fraction (MUGA/Echocardiogram)	X	x i					
Bone marrow biopsy/aspirate g	X				X	X	
Adverse Event Reporting	Recorded from the first dose of study drug through 30 days after last dose of study drug						
Survival h							X

a Screening procedures to occur up to 14 days before Cycle 1 Week 1 Visit, except for pregnancy test (within 7 days prior to Week 1 Visit).

b Perform end-of-study procedures 4 weeks after study completion or at time of early withdrawal. If study procedure cannot be performed on the scheduled day, the procedure must be performed within 48 hours.

c Height will be measured at Screening only.

d Weight will be checked on day 1 of every cycle

e Including albumin, total protein, total bilirubin, ALT, AST, LDH, alkaline phosphatase, bicarbonate, sodium, potassium, chloride, creatinine, BUN, and glucose.

f Serum  $\beta$ HCG pregnancy test in female patients of childbearing potential does not need to be repeated for Cycle 1 Week 1 Visit if the screening test was completed within 72 hours of Cycle 1 Week 1.

g Bone marrow aspirate and/or biopsy and cytogenetics must be performed within 4 weeks prior to Week 1 Visit. Bone marrow biopsies at week 4  $\pm$ 3 days

h Patients will be followed monthly until progression and then annually for survival.

i For cycle 2 only

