## **3. STUDY DESIGN**

In this phase I study, escalating doses of ixazomib will be combined with a fixed dose VXD regimen. Ixazomib will be administered on day 1, 8, and 15. If the patient experiences a DLT the dose of MLN maybe reduced to the next dose level on day 8 or day 15 in that patient. DLT would be any grade 3 or more toxicity which is

thought to be probably or definitely related to ixazomib. Three patients will be treated per dose level unless dose limiting toxicity (DLT) is observed. The starting dose of ixazomib will be 2.3 mg orally on days 1, 8 and 15. If toxicity is seen at this level then dose may be reduced to 1.5 mg (dose level -1). If no DLT is seen in the first 3 patients, the dose will be increased to 3 mg and then to 4 mg orally on days 1, 8 and 15 in a classic 3 +3 phase I design. The study will not attempt to increase the dose beyond 4 mg orally which, if achieved with acceptable toxicity, would be accepted as the recommended phase 2 dose (RP2D). 0 of 3 DLTs would allow escalation to the next dose level. 1 of 3 DLTs will require expanding to six patients; 1 of 6 DLTs will allow escalation again. Two DLTs will require dose de-escalation. Given that the liver toxicity with the VXLD + ixazomib was attributed to pegaspargase and it is eliminated from this protocol, we will start at dose level 1 of 2.3 mg. The maximum tolerated dose (MTD) will be the highest dose administered at which no more than 1 DLT was observed. All patients will be evaluated for hematopoietic stem cell transplantation. If patients achieve CR and are eligible for HSCT, they will proceed to HSCT. If they are not eligible, no donor is identified or if HSCT will be delayed, and the patient has achieved benefit, then treatment may be repeated at the discretion of the investigator. A total of 9-18 patients will be enrolled on the study. The study duration will be about 2 years. The DLT observation period will be from first dose of MLN9708 to 28 days after the first dose. Dose escalation to a higher dose level will require the last patient on the previous dose level to be out of the DLT observation period.

Patients will be offered an opportunity to provide samples to the institutional bank for use in future research.

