## 4.2 Exclusion Criteria

Patients meeting any of the following exclusion criteria are not to be enrolled in the study:

- Patients who are Ph+ ALL who are naive to therapy with an approved tyrosine kinase inhibitor.
- Prior exposure to  $\geq 350$  mg/m^2 of anthracycline (in doxorubicin equivalent dosing), or left ventricular fractional shortening less than 50%.
- Failure to have fully recovered (ie,  $\leq$  Grade 2 toxicity) from the effects of prior chemotherapy regardless of the interval since last treatment.
- Major surgery within 14 days before enrollment.
- Chemotherapy in the last 14 days. (Steroids or Intrathecal chemotherapy will be allowed).
- Systemic treatment, within 7 days before study enrollment, with strong inhibitors of CYP1A2 (fluvoxamine, enoxacin, ciprofloxacin), strong inhibitors of CYP3A (clarithromycin, telithromycin, itraconazole, voriconazole, ketoconazole, nefazodone, posaconazole) or strong CYP3A

inducers (rifampin, rifapentine, rifabutin, carbamazepine, phenytoin, phenobarbital), or use of Ginkgo biloba or St. John's wort.

- Uncontrolled intercurrent illness including, but not limited to ongoing or active infection, symptomatic congestive heart failure, or psychiatric illness/social situations that would limit compliance with study requirements. Patients receiving intravenous antibiotics for infections that are under control may be included in this study.
- Known allergy to any of the study medications, their analogues, or excipients in the various formulations of any agent.
- Inability to swallow oral medication, inability or unwillingness to comply with the drug administration requirements, or GI procedure that could interfere with the oral absorption or tolerance of treatment.
- Diagnosed or treated for another malignancy within 2 years before study enrollment or previously diagnosed with another malignancy and have any evidence of residual disease. Patients with nonmelanoma skin cancer or carcinoma in situ of any type are not excluded if they have undergone complete resection.
- Patient has  $\geq$  Grade 2 peripheral neuropathy.
- Participation in clinical trials with other investigational agents not included in this trial, within 14 days of the start of this trial and throughout the duration of this trial.
- Female patients who are breastfeeding or have a positive serum pregnancy test during the screening period or a positive urine pregnancy test on Day 1 before first dose of study drug.

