## **5. TREATMENT PLAN**

All patients will start therapy within 4 weeks from the bone marrow biopsy.

Lumbar puncture with intrathecal chemotherapy will be performed on all patients on day 1 (+/-1 day) to evaluate for disease.

BM or peripheral blood blast will be collected for correlative studies (optional) prior to starting therapy. Details of therapy are as follows:

Vincristine 1.5 mg/m^2 to a maximum dose of 2 mg IV on days 1, 8, 15 and 22

Dexamethasone 10 mg/m^2 orally or intravenously on days 1-14

Doxorubicin 60 mg/m^2 on day 1 by IV bolus.

For patients without CNS involvement:

-Cytarabine 100 mg will be administered intrathecally on day 1 (+/-1 day)  
(cytarabine dose should be reduced to 50 mg if given through a central ommaya reservoir)

-Methotrexate 12 mg will be administered intrathecally on day 8 (+/-1 day)

For patients with CNS involvement:

-Cytarabine 100 mg will be administered intrathecally on day 1 (+/-1 day)  
(cytarabine dose should be reduced to 50 mg if given through a central ommaya reservoir)

-Triple intrathecal chemotherapy with cytarabine 30 mg, methotrexate 15 mg and hydrocortisone 15 mg on (Day 8, 15 and 22 (+/-1 day)).

A bone marrow biopsy/aspirate will be performed at D28 +/- 3 days. For patients in remission, and have an available donor for HCT should proceed to HCT and be removed from the protocol treatment. Patients will still be followed for survival and progression free survival. A second cycle of treatment may be administered at the investigators discretion.

Ixazomib will be administered orally once weekly on day 1, 8 and 15. The first 3 patients will receive 2.3 mg orally (dose level 1). Dose escalation or de-escalation

will then proceed as previously detailed. There will be no inpatient dose escalation.

Table (7) Ixazomib dosing

	Day	Oral Dosing (mg)
Dose level -1	1, 8, 15	1.5
Dose level 1	1, 8, 15	2.3
Dose level 2	1, 8, 15	3
Dose level 3	1, 8, 15	4

Supportive care:

All patients will receive antibacterial, antiviral, antifungal and pneumocystis carinii pneumonia (PCP) prophylaxis. Prophylaxis regimen may follow institutional guidelines. The following prophylaxis may be used as guidelines:

Quinolones for antibacterial prophylaxis e.g., levofloxacin 500 mg orally daily

Antiviral prophylaxis: acyclovir 800 mg orally twice daily

Antifungal prophylaxis: Fluconazole 400 mg orally daily, or Liposomal Amphotericin B 9 mg/kg IV once per week or Caspofungin 50 mg IV /daily

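### The cardiac exclusion sets its 50% limit on fractional shortening, but the schedule measures ejection fraction, so eligibility depends on which was meant

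*Combined protocol and SAP*

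**What the plan says.** **Entry limit.** The exclusion criteria in the Protocol Summary, repeated in Section 4.2, rule out prior anthracycline of 350 mg/m² or more (doxorubicin equivalent) "or left ventricular fractional shortening less than 50" per cent.

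**Cardiac test.** The one cardiac row in the Schedule of Events is "Cardiac Ejection Fraction (MUGA/Echocardiogram"). It is marked at screening and again in the week 1 column for cycles 1 and 2, where footnote i reads "For cycle 2 only". The schedule does not mention fractional shortening.

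**Repeat treatment.** Section 3 says "then treatment may be repeated at the discretion of the investigator". The parallel Summary sentence says "then treatment may be repeated for another cycle as clinically indicated", and Section 5 says "A second cycle of treatment may be administered at the investigators discretion". Doxorubicin 60 mg/m² is given "on day 1 by IV bolus" (Section 5).

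**Rules for a new cycle.** Section 7.5 requires neutrophil and platelet recovery (unless the cytopenias are due to disease) and nonhematologic toxicity back to Grade 1 or less, or to baseline. Otherwise treatment is held. Section 15.2 counts a clinically relevant worsening of a clinical finding as an adverse event.

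**The concern.** An eligibility limit works only if the measured quantity is the one that is limited. Here the criterion names fractional shortening, a proportional change in ventricular diameter. The schedule asks for ejection fraction, a proportional change in volume. A 50% cut on one is not a 50% cut on the other.

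Two sites, or two investigators at one site, could therefore treat the same screening result differently. One might compare the ejection fraction with 50% and enrol the patient. Another might apply the written rule and exclude the same patient. The first would also have enrolled in breach of the criterion as written. The wording is the same in both places, so neither section corrects the other.

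The criterion guards entry to a regimen containing doxorubicin, for which Section 6.3 lists reduced LVEF and heart failure as delayed effects. It also helps define the population to which the tolerability results and the response rate apply, in a trial of only 9 to 18 patients.

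**Working it through.** The plan gives no conversion or figure of its own to reproduce. The check compares the two measures, then reads the sections on repeat treatment side by side.

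**1. Inputs from the documents.** Limit: 50%, on fractional shortening (Summary exclusion criteria; Section 4.2). Scheduled measure: ejection fraction (Schedule of Events).

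**2. Assumption, not in the documents.** Ventricular volume is proportional to diameter to the power k. Take k = 2 if length stays fixed, and k = 3 if shortening is equal in all directions.

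**3. Formula.** Fractional shortening (FS) is the share of diameter lost in contraction, so end-systolic diameter is (1 − FS) times end-diastolic diameter, and the volumes stand in the ratio (1 − FS)^k. Ejection fraction (EF) is the share of volume lost:

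- EF = 1 − (1 − FS)^k
- inverse: FS = 1 − (1 − EF)^(1/k)

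**4. Results.**

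| | k = 2 | k = 3 |
|---|---|---|
| EF at FS = 50% | 1 − 0.50² = 1 − 0.25 = 75% | 1 − 0.50³ = 1 − 0.125 = 87.5% |
| FS at EF = 50% | 1 − 0.7071 = 29.3% | 1 − 0.7937 = 20.6% |

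**5. Who is affected.** The literal rule excludes EF below 75% (k = 2) or below 87.5% (k = 3). An ejection fraction rule at 50% excludes only EF below 50%. The two rules disagree for EF from 50% up to 75%, a band of 25 points, or up to 87.5%, a band of 37.5 points. In that band the literal rule is always the stricter one.

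**6. Repeat cycles, side by side.**

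| Place | Number of cycles |
|---|---|
| Section 3 | not stated |
| Protocol Summary | one further, so two |
| Section 5 | a second, so two |
| Schedule of Events | cycles 1 and 2 |

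Three places agree and the fourth is silent. Two cycles give 2 × 60 = 120 mg/m² of doxorubicin on study, with two scheduled cardiac tests (screening and cycle 2).

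**The case against.** **On the entry limit.** Echocardiography, one of the two scheduled methods, can also yield fractional shortening, so the criterion is not untestable. The ranges of 75% to 87.5% and 20.6% to 29.3% come entirely from an assumed geometry and should not be taken as measured limits for this trial. Both points stand. They do not remove the mismatch: the schedule asks for ejection fraction, and the criterion limits something else. The assumption affects the width of the disputed band, not the fact that two different quantities are named.

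**Stronger readings that a reader might infer, and why they fail.**

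- *A third cycle is allowed, with 3 × 60 = 180 mg/m² and no cardiac test before the third dose.* This needs Section 3 to be read alone. The Summary, Section 5 and the schedule all point to two cycles, and Section 3 states no different number.
- *The cycle 2 cardiac test might follow the doxorubicin.* Its column most naturally means the start of the cycle. It is tempting to contrast Section 4.2, which excludes patients with "a positive urine pregnancy test on Day 1 before first dose of study drug", but that is an entry criterion and not a schedule row. The blood count and chemistry rows have no stated order against that day's dose either.
- *The plan has no cardiac safeguard for cycle 2.* The screening test supplies a baseline. Section 15.2 makes a clinically relevant fall an adverse event, and Section 7.5 holds treatment until nonhematologic toxicity has resolved. An explicit pass value would be a preference, and nothing in the documents says that it should equal the entry limit.

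**Conclusion.** The entry limit is wrong as written: it places a decision threshold on a measure that the schedule does not name. Under the stated assumption, the literal rule excludes patients with ejection fraction from 50% up to 75% at the least and 87.5% at the most, all of whom would be eligible if 50% was meant for ejection fraction. The documents do not show which was meant, how sites apply the rule, or how many patients fall in the band.

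The weight is minor to moderate. The point concerns who may enter. It does not show that the first-cycle escalation decisions or the MTD are affected, or that any cumulative anthracycline dose is unsafe. The missing cycle number in Section 3 and the unstated order of the cycle 2 test are clarifications only.

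**What to change.** In the Protocol Summary exclusion criteria and in Section 4.2, replace fractional shortening with left ventricular ejection fraction, keeping the limit at less than 50%. The sponsor should confirm that 50% was meant for ejection fraction. If fractional shortening was truly intended, the schedule should name it and the 50% value should be confirmed for that measure instead.

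The cost is a wording change in two places, with no new procedure, visit or sample, because ejection fraction is already measured at screening. The downside is that, if sites now apply the literal text, more patients become eligible. That is why the value needs confirming and should not be assumed.

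Two optional clarifications can go in the same amendment: state a maximum of two cycles in Section 3, and state in schedule footnote i that the cycle 2 cardiac test precedes the day 1 doxorubicin. The second could delay that dose if a result is late.

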#### **4. STUDY POPULATION**

##### **4.1 Inclusion Criteria**

Each patient must meet all of the following inclusion criteria to be enrolled in the study:

- Male or female patients 18 years or older
- Have relapsed B or T-precursor acute lymphocytic leukemia/lymphoma, lymphoblastic lymphoma or mixed phenotype acute leukemia with increased bone marrow or peripheral blood blasts by morphology with or without CNS involvement
- Prior therapy: At least two prior treatment attempts to induce remission with no limit on the number of prior treatment regimens.
- Patients are eligible after allogeneic stem cell transplantation
- Eastern Cooperative Oncology Group (ECOG) performance status 0-2
- Patients must meet the following clinical laboratory criteria:
  - Total bilirubin  $\leq 1.5 \times$  the upper limit of the normal range (ULN).
  - Alanine aminotransferase (ALT) and aspartate aminotransferase (AST)  $\leq 3 \times$  ULN.
  - Calculated creatinine clearance  $\geq 30$  mL/min
  - Absolute neutrophil count (ANC)  $> 1,000$ /cmm and platelets  $> 75,000$ /cmm unless the cytopenias are secondary to disease
- Life expectancy reasonably adequate for evaluating the treatment effect
- Patients must be at least 2 weeks from major surgery, radiation therapy, participation in other investigational trials and have recovered from clinically significant toxicities of these prior treatments
- Female patients who:
  - Are postmenopausal for at least 1 year before the screening visit, OR
  - Are surgically sterile, OR
  - If they are of childbearing potential, agree to practice 2 effective methods of contraception, at the same time, from the time of signing the informed consent form through 90 days after the last dose of study drug, OR
  - Agree to practice true abstinence when this is in line with the preferred and usual lifestyle of the subject. (Periodic abstinence [eg, calendar, ovulation, symptothermal, post-ovulation methods] and withdrawal are not acceptable methods of contraception.)

- Male patients, even if surgically sterilized (ie, status post-vasectomy), must agree to one of the following:
  - Agree to practice effective barrier contraception during the entire study treatment period and through 90 days after the last dose of study drug, OR
  - Agree to practice true abstinence when this is in line with the preferred and usual lifestyle of the subject. (Periodic abstinence (eg, calendar, ovulation, symptothermal, post-ovulation methods] and withdrawal are not acceptable methods of contraception.).

